- Update on eligibility checklist (within IRT) to be completed on C1D1 (prior to first dose) instead of screening;
- Addition of “Abdominal Girth” being part of metabolic syndrome (metabolic syndrome is a clustering of hyperglycemia/insulin resistance, obesity and dyslipidemia and is

important for several reasons, including identification of patients who are at high risk of developing atherosclerotic cardiovascular disease and type 2 diabetes);

- Removal of “Fasting Glucose” and addition of “Fasting Plasma Glucose” at Cycle 3 Day 1, Cycle 3 Day 8, Cycle 4 Day 1 to Cycle 12 Day 1 and at EOT;
- Addition of HbA1C at Cycle 3 Day 1,
- Alpelisib start day has been updated from Cycle 1 Day 1 to Cycle 1 Day 8;
- Frequency of administration of metformin XR and dapagliflozin plus metformin XR has been corrected to once daily;
- Footnote number 3 and footnote number 4 have been updated.
- Section 8.1.2: Correction on the data collection for screen failures has been performed.
- Section 8.2: Addition of abdominal girth.
- Table 8-3: Footnote number 1 has been updated with regards to tumor evaluation at End of Treatment which has to be conducted in absence of progressive disease at previous tumor assessment and if this tumor assessment was done more than 21 days prior to EOT visit (previously 28 days). Footnote number 2 has been removed as the same language is present in the corresponding section of the protocol.
- Table 8-4: Abdominal girth added.

■ [REDACTED]

- Section 8.4.1: The language for alternative laboratory collection has been updated based on new COVID-19 Guidance for CTTs - Protocols and Amendments for New and Ongoing Studies (Version 5.0).

■ [REDACTED]

- Section 10.1.3 has been updated with the requirements on SAE follow-up reporting.
- Section 12.5.1: Updated summary measure for PFS to PFS rate at 24 weeks and 48 weeks, corresponding to 6 and 12 cycles.

■ [REDACTED]

- Section 12.7: Timepoint for statistical testing of the primary endpoint has been removed.
- Section 15: Updated with additional references used in the protocol.
- Appendix 16.1: Table 16-3 was updated to align with dose modification table (Table 6-3).

In addition, editorial changes and text corrections were made for clarification in sections of the protocol, as appropriate/required.

■ [REDACTED]

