### 6.6.1 Dose modifications

For participants who do not tolerate the protocol-specified dosing schedule, dose interruptions, and/or reductions are either recommended or mandated in order to allow participants to continue the study treatment.

These dose modifications are summarized in [Table 6-3](#). Deviations to mandatory dose interruptions and/or reductions are not allowed. Permanent discontinuation from study treatment is mandatory for specific events indicated as such in [Table 6-3](#) or listed in [Section 9.1](#).

These dose changes must be recorded on the appropriate eCRF.

Additionally dose escalations of antihyperglycemic medication as described in [Section 6.6.2](#) must also be recorded on the appropriate eCRF.

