#### 6.6.1.1 Alpelisib dose modifications

Recommendations for dose reduction or dose interruption of alpelisib in the management of adverse reactions are summarized in [Table 6-3](#). Adverse events for alpelisib are graded according to CTCAE v4.03 since this version is more objective than CTCAE v5 with regard to hyperglycemia grading as it is based on laboratory values. Clinical judgment of the treating physician, including confirmation of laboratory values if deemed necessary, should guide the management plan of each participant based on individual benefit/risk assessment.

A maximum of 2 dose reductions of alpelisib will be allowed after which treatment must be discontinued as indicated in [Section 6.3.2.1](#). Deviations to stepwise dose reductions are not allowed.

After treatment is resumed at a lower dose:

- If the same toxicity reoccurs with the same severity, then the next treatment re-initiation must resume at a lower dose irrespective of duration, except if specified in [Table 6-3](#).
- Once the alpelisib dose has been reduced by the Investigator, no re-escalation is allowed, even upon resolution of AE.

If a participant requires a withholding of alpelisib dose, the participant may continue fulvestrant, per Investigator discretion. As the half-life of alpelisib is approximately 9 hours, if alpelisib is interrupted, then consideration should be given to any antihyperglycemic medications. All scheduled assessments will continue to be performed as per protocol.

Permanent discontinuation of alpelisib treatment is mandatory for specific events indicated as such in [Table 6-3](#) or listed in [Section 9.1](#). These dose changes must be recorded on the appropriate eCRF.

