Grade 4 (FG > 500 mg/dL) [> 27.8 mmol/L]	
 
Omit alpelisib, confirm fasting status of the assessment. If non-fasting, re-check within 24 hours.
 
 
Regardless of fasting status, consider IV fluids.
 
 
Exclude confounding factors like e.g., urinary tract infection.
 
Consult with diabetologist, initiate or intensify medication with appropriate antihyperglycemic treatment (see Grade 3), re-check within 24 hours.
 
If grade improves then follow specific grade recommendations
 
If FG is confirmed as > 500 mg/dL and confounding factors could be excluded, permanently discontinue participant from alpelisib.
 

CTCAE v 4.03 is modified to allow fasting blood glucose values in addition to fasting plasma glucose values.	
Investigations (Hepatic) . Note: this is for newly occurred or worsened from baseline	
Isolated total Bilirubin elevation	
Grade 1 (> ULN - 1.5 x ULN)	
 
No dose adjustment is required. Initiate appropriate medical therapy and monitor as clinically indicated.
 

Grade 2 (> 1.5 - 3.0 x ULN)	
 
Interrupt dose until recovery to Grade ≤ 1 and resume at the same dose if resolved in ≤ 14 days or resume at the next lower dose level if resolved in > 14 days.
 

Worst toxicity - CTCAE grade (value)	Dose Modifications for alpelisib
Grade 3 (> 3.0 - 10.0 x ULN)	
 
Interrupt dose until recovery to Grade ≤ 1, then resume at the next lower dose level.
 

Grade 4 (> 10.0 x ULN)	
 
Permanently discontinue.
 

Isolated AST or ALT elevation	
Grade 1 (> ULN - 3.0 x ULN) Grade 2 (> 3.0 - 5.0 x ULN)	
 
No dose adjustment is required. Initiate appropriate medical therapy and monitor as clinically indicated.
 

Grade 3 (> 5.0 - 20.0 x ULN)	
 
Interrupt dose until recovery to Grade ≤ 1, then decrease dose level.
 

Grade 4 (> 20.0 x ULN)	
 
Permanently discontinue.
 

Combined ALT/AST and TBIL elevation	

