**Table 16-2 Follow up requirements for liver laboratory triggers - ALT, AST, TBIL -**

ALT	TBIL	Liver Symptoms	Action
ALT increase without bilirubin increase:			
If normal at baseline: ALT $> 3 \times$ ULN	Normal For participants with Gilbert's syndrome: No change in baseline TBIL	None	
 
• No change to study treatment
 
• Measure ALT, AST, ALP, GGT, total bilirubin (TBIL), INR, albumin, CK, and GLDH in 48-72 hours.
 
• Follow-up for symptoms.
 

If elevated at baseline: ALT $> 2 \times$ baseline or $> 300$ U/L (whichever occurs first)			
If normal at baseline: ALT $> 5 \times$ ULN for more than two weeks	Normal For participants with Gilbert's syndrome: No change in baseline TBIL	None	
If elevated at baseline: ALT $> 3 \times$ baseline or $> 300$ U/L (whichever occurs first) for more than two weeks			
 
• Interrupt study drug
 
• Measure ALT, AST, ALP, GGT, TBIL, INR, albumin, CK, and GLDH in 48-72 hours.
 
• Follow-up for symptoms.
 

If normal at baseline:	Normal	None	

ALT	TBIL	Liver Symptoms	Action
ALT > 8 x ULN			
ALT increase with bilirubin increase:			
If normal at baseline: ALT > 3 x ULN	TBIL > 2 x ULN (or INR > 1.5) For participants with Gilbert's syndrome: Doubling of direct bilirubin	None	
 
Initiate close monitoring and workup for competing etiologies.
 
Study drug can be restarted only if another etiology is identified and liver enzymes return to baseline.
 

If elevated at baseline: ALT > 2 x baseline or > 300 U/L (whichever occurs first)			
If normal at baseline: ALT > 3 x ULN		Severe fatigue, nausea, vomiting, right upper quadrant pain	
If elevated at baseline: ALT > 2 x baseline or > 300 U/L (whichever occurs first)	Normal or elevated		

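### For isolated ALT above 5 and up to 8 × ULN with normal baseline, Table 6-3 says interrupt and reduce, Table 16-2 says no change for up to two weeks, and neither is ranked first

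*Protocol*

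**What the plan says.** Protocol Table 6-3 (isolated AST or ALT elevation) asks for no dose adjustment in Grades 1 and 2, that is, up to 5 × ULN. For Grade 3, above 5 and up to 20 × ULN, the instruction is "Interrupt dose until recovery to Grade ≤ 1, then decrease dose level". No duration is attached.

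Protocol Table 16-2 (Appendix 1) covers an ALT rise without a bilirubin rise and without liver symptoms. For a normal baseline, its first row applies above 3 × ULN, has no upper bound, and carries the action "No change to study treatment", plus repeat liver tests in 48 to 72 hours and symptom follow-up. The next normal-baseline row is reached when ALT exceeds 5 × "ULN for more than two weeks". A further row, without a duration condition, starts above 8 × ULN. These later rows lead to interruption.

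On the standing of Table 6-3, Section 6.6.1 says that "dose interruptions, and/or reductions are either recommended or mandated" and bars deviation from the mandatory ones, but does not mark the Grade 3 ALT entry as one or the other. Section 6.6.1.1 calls the Table 6-3 entries recommendations and gives clinical judgment a role in management. Section 10.2.1 sends liver events to Appendix 1 and, once an elevation is confirmed, asks for close observation and for interruption to be considered.

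**The concern.** Table 16-1 lists ALT or AST above 5 × ULN as a liver trigger, and Section 10.2.1 says such events should be followed up. Table 16-2 then sets out the follow-up. The value that makes Table 6-3 interrupt therefore also sends the site to a table that tells it to continue.

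Two sites could handle the same ALT differently. One would stop alpelisib and resume a level lower, for example 250 mg after 300 mg (Table 6-2). The other would stay at 300 mg while it waits. The difference lasts: Section 6.6.1.1 forbids re-escalation and allows only two reductions. At stake are participant safety and the consistency of the alpelisib interruptions and reductions that SAP Section 2.4.1 plans to list.

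**Working it through.** The plan states no figure to reproduce, and no sample size, alpha or power calculation is involved. The check sets the two tables side by side for normal baseline, normal bilirubin and no symptoms, and then looks for a ranking.

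| Isolated ALT | Table 6-3 | Table 16-2 | Agree on interruption? |
|---|---|---|---|
| > 3 to 5 × ULN | Grade 2: no dose adjustment | No change, repeat panel | Yes |
| > 5 to 8 × ULN, up to two weeks | Grade 3: interrupt, then one level lower | Only the > 3 × ULN row is met: no change, repeat panel | **No** |
| > 5 to 8 × ULN, more than two weeks | Grade 3: as above | Interrupt | Yes |
| > 8 to 20 × ULN | Grade 3: as above | Interrupt, no duration condition | Yes |

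The tables disagree in one cell: above 5 and up to 8 × ULN, for up to 14 days.

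Table 16-2 is broken in the extracted text. The action cells beside the > 5 × ULN and > 8 × ULN normal-baseline rows are blank and are read as merged with the neighbouring interrupt action. The conflict does not depend on this, because the > 3 × ULN row is explicit and unbounded above. Only the upper edge at 8 × ULN and the end of the conflict after two weeks rest on it.

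Sections that might settle the order:

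- **6.1.4** refers continuation of treatment to 6.6.1, and **8** refers delays for toxicity to 6.6.1.1. Both favour Table 6-3. Neither mentions Appendix 1.
- **6.6.1** makes Table 6-3 the summary of dose modifications and bars deviation from mandatory ones. It does not say which ALT/AST interruptions are mandatory or name Table 16-2.
- **6.6.1.1** calls the entries recommendations.
- **10.2.1** leaves interruption to be considered as appropriate and gives no ranking.

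A reader can infer that Table 6-3 leads, but no sentence says so.

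**The case against.** The strongest reply is that precedence is already settled in substance. Section 6.6.1 is the dosing section and other sections point to it, while Appendix 1 is about follow-up. If the Grade 3 interruption is mandatory, 6.6.1 forbids departing from it. If it is only recommended, clinical judgment applies and there is no hard conflict. This stands in part: the lean toward Table 6-3 is real, and the documents do not show the Grade 3 interruption to be mandatory. But Table 16-2 carries its own dosing instruction, and a site should not have to infer which one to follow for a liver stopping rule.

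It is also fair that the no-change row is not unmonitored: it requires repeat tests in 48 to 72 hours, and severe symptoms or a marked bilirubin or INR rise move the participant to stricter rows.

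A reader might infer four stronger points. The documents do not support them:

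- **That Table 16-2 also permits no change above 5 × ULN whenever baseline ALT is elevated.** Its first elevated-baseline row starts at the lower of 2 × baseline and 300 U/L. With the ALT upper limit of 35 U/L in SAP Section 5.3, 300/35 = 8.6 × ULN. At a baseline of 3 × ULN the row starts at min(2 × 3, 8.6) = 6.0 × ULN. Between 5 and 6 × ULN the table is silent, not permissive. With that limit, the same happens over part of the range for any baseline above 2.5 × ULN.
- **That a site could restart alpelisib after ALT above 20 × ULN.** Table 6-3 discontinues permanently at Grade 4, and Section 6.6.1.1 says "Permanent discontinuation of alpelisib treatment is mandatory for specific events indicated as such in" that table. Silence in Table 16-2 does not override this.
- **That "Study drug can be restarted only if another etiology is identified and liver enzymes return to baseline" binds isolated ALT rises.** In the extract this text stands beside the rows with a bilirubin rise. Applying it to isolated ALT is a guess about merged cells.
- **That the band is a fifth of the problem.** Three of fifteen ULN multiples, (8 − 5)/(20 − 5), is the width of an interval, not a share of participants or of risk.

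**Conclusion.** The point holds in a narrow form. For normal baseline ALT, normal bilirubin and no liver symptoms, ALT above 5 and up to 8 × ULN lasting up to two weeks gets contradictory dosing instructions, and no sentence ranks the two tables. The consequence is up to 14 days at an unchanged dose against interruption followed by a reduction that cannot be reversed.

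No expected number of participants can be given, because the documents report no laboratory ALT rates. The SAP (Section 1) records a permanent halt of recruitment and early termination, so the effect is limited to any participants still on alpelisib. The primary endpoint, alpha and power are unaffected.

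The conclusion assumes that the > 3 × ULN row and its action are correctly extracted, and that the later normal-baseline rows share the interrupt action. It does not assume that the Grade 3 interruption is mandatory.

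**What to change.** Two edits, by written amendment:

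1. In Table 16-2, remove the two-week condition from the normal-baseline > 5 × ULN row, so that study drug is interrupted at > 5 × ULN.
2. In Section 6.6.1, add: *For isolated ALT or AST elevation, Table 6-3 governs alpelisib interruption, dose reduction, resumption and discontinuation if Appendix 1 differs.*

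Table 6-3 stays as it is. The added sentence should not preserve the Table 16-2 restart conditions for isolated ALT. Table 6-3 allows resumption at a lower level after recovery to Grade 1 or better, so keeping a stricter restart rule beside it would create a new contradiction. Because the sentence is not limited to normal baseline, it also settles isolated elevations from a raised baseline.

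The cost is an amendment with the approvals in Section 14.1 and no new procedures. The downside is a few more early interruptions for isolated ALT rises that would have been transient.

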For participants with normal ALT and AST and total bilirubin value at baseline: AST or ALT > 3.0 x upper limit of normal (ULN) combined with total bilirubin > 2.0 x ULN without evidence of cholestasis  For participants with elevated AST or ALT or total bilirubin value at baseline: [AST or ALT > 3.0 x baseline] or [ALT or AST > 8.0 x ULN], whichever occurs first, combined with [total bilirubin > 2.0 x baseline AND > 2.0 x ULN]  Note: For participants with Gilbert's syndrome, at least 2-fold increase in direct bilirubin.	
 
Interrupt treatment and adjudicate for DILI: Repeat as soon as possible, preferably within 48 hours from awareness of the abnormal results, then with weekly monitoring of LFTsb, or as clinically indicated, until AST, ALT, or total bilirubin have resolved ≤ ULN or to baseline. (Refer to the Section 6.6.3.1 for additional follow-up evaluations as applicable.) 
 
If causality assessment indicates that DILI is probable: Permanently discontinue participant from treatment.
 
If not DILI: Treat the identified cause according to institutional guidelines. Once resolved, reduce by one dose level.
 
 
 

Gastrointestinal	
Diarrhea is defined as: a disorder characterized by frequent and watery bowel movements.	
Grade 1 (Increase of < 4 stools per day over baseline; mild increase in ostomy output compared to baseline)	
 
Maintain dose level but initiate appropriate medical therapy and monitor as clinically indicated.
 

Grade 2 (Increase of 4 - 6 stools per day over baseline; moderate increase in ostomy output compared to baseline; limiting instrumental Activities of Daily Living (ADL))	
 
Omit dose until resolved to ≤ Grade 1, then restart at same dose.
 
If diarrhea returns as ≥ Grade 2, then omit dose until resolved to ≤ Grade 1, then decrease 1 dose level
 
Initiate or intensify appropriate medical therapy and monitor as clinically indicated.
 

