**Table 6-6 Alternative causes of liver disease**

Disease	Assessment
Hepatitis A, B, C, E	

IgM anti-HAV; HBsAg, IgM & IgG anti-HBc, HBV DNA; anti-HCV, HCV RNA, IgM & IgG anti-HEV, HEV RNA

CMV, HSV, EBV infection	

IgM & IgG anti-CMV, IgM & IgG anti-HSV; IgM & IgG anti-EBV

Autoimmune hepatitis	

Antinuclear Antibodies (ANA) & Anti-Smooth Muscle Antibody (ASMA) titers, total IgM, IgG, IgE, IgA

Alcoholic hepatitis	

Ethanol history, GGT, MCV, carbohydrate-deficient (CD)-transferrin

Nonalcoholic steatohepatitis	

Ultrasound or MRI

Hypoxic/ischemic hepatopathy	

Medical history: acute or chronic congestive heart failure, hypotension, hypoxia, hepatic venous occlusion. Ultrasound or MRI.

Biliary tract disease	

Ultrasound or MRI, ERCP as appropriate.

Wilson disease (if < 40 yrs old)	

Caeruloplasmin

Hemochromatosis	

Ferritin, transferrin

Alpha-1-antitrypsin deficiency	

Alpha-1-antitrypsin

Other causes should also be considered based upon participants' medical history (hyperthyroidism / thyrotoxic hepatitis – T3, T4, Thyroid-stimulating hormone; cardiovascular disease / ischemic hepatitis – ECG, prior hypotensive episodes; glycogenic hepatitis).

If DILI confirmed: permanently discontinue study treatment.

If DILI is unlikely: interrupt treatment. Treat identified cause according to institutional guidelines. If resolved, reduce by one dose level. Re-administration of study treatment should be considered only if the investigator assesses benefit to outweigh the risk. Any decision regarding re-administration of study drug/s and dose regimen should be discussed with the Novartis medical safety team.

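### After a combined ALT/AST and bilirubin elevation, Table 6-3, Section 6.6.3.1 and Table 16-2 give different conditions for re-administration, and none is named as governing

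*Protocol*

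**What the plan says.** Three places in the protocol deal with this event.

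- **Table 6-3, row for combined ALT/AST and TBIL elevation.** Treatment is interrupted, the case is adjudicated for drug-induced liver injury (DILI), and liver tests are repeated and then followed weekly "until AST, ALT, or total bilirubin have resolved ≤ ULN or to baseline". There are two branches. One reads "If causality assessment indicates that DILI is probable: Permanently discontinue participant from treatment". The other reads "If not DILI: Treat the identified cause according to institutional guidelines. Once resolved, reduce by one dose level". The cell points to Section 6.6.3.1 for additional follow-up evaluations.
- **Section 6.6.3.1, text below Table 6-6.** The stop rule is "If DILI confirmed: permanently discontinue study treatment". If DILI is unlikely, treatment is interrupted, the cause is treated and, if the event resolves, the dose goes down one level. Re-administration is to be considered only if the investigator finds that benefit exceeds risk, and "Any decision regarding re-administration of study drug/s and dose regimen should be discussed with the Novartis medical safety team". The next paragraph defines *probable* as more than 50% likely and reserves the label DILI for such cases.
- **Appendix 1, Table 16-2, rows for an ALT increase with a bilirubin increase.** These call for close monitoring and a search for competing causes, and then state "Study drug can be restarted only if another etiology is identified and liver enzymes return to baseline".

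On precedence, Section 6.6.1 says that permanent discontinuation is mandatory for events so marked in Table 6-3 or listed in Section 9.1. Section 9.1.1 refers to Section 6.6.3. Section 10.2.1 refers liver events to the tables in Appendix 1. No sentence says which text prevails.

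**The concern.** A combined transaminase and bilirubin rise without cholestasis is what the protocol treats as a potential Hy's Law case. An investigator can reach any of the three texts through a proper cross-reference. If they set different conditions for giving drug again, sites can handle the same participant differently while each believes it is following the protocol. The points at issue are whether the sponsor's safety team is consulted before re-exposure and how far the liver tests must have recovered.

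The data are touched as well. Interruptions, reductions and duration of exposure are tolerability endpoints in Table 2-1, so differing restart practice between sites would show up in them. The primary estimand remains defined, because it handles interruption and discontinuation of alpelisib by treatment policy.

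**Working it through.** There is no figure in the plan to reproduce, and no rate, margin or power is involved. The check sets the texts side by side.

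**Step 1: do all three apply to one event?** Take a participant with normal ALT, AST and bilirubin at baseline. Table 6-3 and Section 6.6.3.1 are triggered by ALT or AST above 3 × ULN with bilirubin above 2 × ULN and no cholestasis. The Table 16-2 rows are triggered by ALT above 3 × ULN with bilirubin above 2 × ULN (or INR above 1.5). An event with ALT and bilirubin above these limits and no cholestasis falls under all three. With elevated baseline values the transaminase thresholds themselves differ (3 × baseline or 8 × ULN, against 2 × baseline or 300 U/L), so the example stays with a normal baseline.

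**Step 2: conditions for giving drug again.**

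| | Table 6-3 | Section 6.6.3.1 | Table 16-2 (restart sentence only) |
|---|---|---|---|
| Causality | not DILI; an identified cause is presupposed | DILI unlikely; an identified cause is presupposed | another cause identified |
| Recovery | resolved; monitoring runs to ULN or baseline | resolved; no level given | enzymes at baseline |
| Benefit-risk judgement specific to restart | not stated | stated | not in the sentence |
| Discussion with sponsor | not stated | stated | not in the sentence |

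The action cells of Table 16-2 are merged in the text available, so nothing is inferred from what seems absent there. Its restart sentence is intact.

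**Step 3: one participant.** Assumed values: ALT at baseline 0.5 × ULN, a non-drug cause identified, ALT now 0.9 × ULN, bilirubin normal. ALT is 0.9 × ULN, hence within normal limits, but 0.9 / 0.5 = 1.8 times the participant's own baseline.

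- Table 6-3: resolved, if *resolved* takes the level given for monitoring. Resume one level lower.
- Section 6.6.3.1: depends on the benefit-risk judgement and the sponsor discussion.
- Table 16-2: read literally, the enzymes are not back at baseline, so no restart.

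**Step 4: how general is this?** Each restart rule was applied literally to 2 (DILI probable or not) × 2 (other cause identified or not) × 3 (recovered to baseline, resolved but not to baseline, not resolved) × 2 (benefit-risk favourable and discussed, or not) = 24 combinations. These count logical cases and are not frequencies. The three rules disagree in 9:

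- 4 have no other cause identified. They disappear if Table 6-3 and Section 6.6.3.1 are read as requiring an identified cause.
- 2 have probable DILI with another cause also found. They depend on Table 16-2 containing no stop instruction, which cannot be judged here.
- 3 have DILI not probable and a cause identified. In one the enzymes are at baseline but the steps in Section 6.6.3.1 are not met. In two the event has resolved, but not to baseline.

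Check: 4 + 2 + 3 = 9. Of the 24 − 9 = 15 combinations in agreement, one permits restart under all three texts (DILI not probable, cause found, enzymes at baseline, benefit-risk favourable and discussed), and 14 bar it under all three.

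**The case against.** The texts are closer than they look.

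- Section 6.6.1.1, which introduces Table 6-3, already asks that management follow individual benefit-risk assessment, so Table 6-3 does not resume dosing free of any such judgement.
- The Table 6-3 cell cites Section 6.6.3.1, and that section covers any decision to re-administer. A site can comply with both, because an added step is not a contradiction.
- Table 16-2 sorts participants into normal or elevated at baseline. For someone who started normal, a return to the normal range is a plausible reading of baseline, and the example in Step 3 would then pass.

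These arguments narrow the point without removing it. The cross-reference in Table 6-3 is for follow-up evaluations and does not mention restart conditions. The duty to discuss with the sponsor stands only in Section 6.6.3.1. The softer reading of Table 16-2 has to be supplied by the reader, while Table 6-3 states ULN and baseline as alternatives. Nothing ranks the three.

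Some stronger readings are tempting and are not supported:

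- *Three different permanent-stop conditions.* Only Table 6-3 and Section 6.6.3.1 visibly state one.
- *A probable but unconfirmed case falls between the rules.* Section 6.6.3.1 itself makes probable, at more than 50%, the definition of a DILI case.
- *Recovery of a single analyte is enough under Table 6-3.* The sentence that lists AST, ALT or bilirubin says how long to monitor; the resumption wording is separate.
- *Only Table 16-2 needs another cause.* The other two both speak of treating an identified one.

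**Conclusion.** The concern holds for re-administration. After the same combined elevation, the three texts differ on whether the sponsor is consulted, on whether a benefit-risk judgement specific to restart is required, and on the recovery level, with no order of precedence. The terms *probable* and *confirmed* for permanent stop are a wording mismatch to align; they do not amount to a conflict of substance.

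Not every such case is affected: the texts agree where the cause is clearly not the drug, enzymes are back at baseline, and benefit-risk is favourable and discussed. The Step 3 result assumes that *resolved* in Table 6-3 takes its monitoring level and that *baseline* in Table 16-2 means the participant's own value. The documents give no rate for these events, so neither their number nor their rarity can be stated. The SAP records a permanent halt of recruitment and early termination, which limits how many participants the text can still govern but does not remove the inconsistency. No view is taken on which clinical rule is right.

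**What to change.** Reconcile Table 6-3, Section 6.6.3.1 and Table 16-2 on three items: the conditions for re-administration, including whether sponsor discussion is required; the recovery level; and the causality wording for permanent stop. Name one of the three as governing and have the other two refer to it. Point Sections 6.6.1, 9.1.1 and 10.2.1 to that text. The sponsor's safety physicians choose the clinical content.

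The cost is wording in one table cell, one paragraph and one appendix cell, plus the cross-references. No procedure, visit or participant is added. Amendment 01 already aligned Table 16-3 with Table 6-3, so doing the same for Table 16-2 would complete that work.
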